3.8 Other Secondary Outcomes: Cost Effectiveness	
3.8.1 Analysis Method:	17
3.9 Secondary Outcomes: Safety Important Medical Events (IME) Adverse Events (Al Serious Adverse Events (SAE)	
3.10 Sensitivity Analyses	17
3.11 Tables and Figures for the Main Paper	18

	3.12	Approval	18
		erences	
Ap	pendix	< 1	28

Abbreviations and definitions of terms

ADRS	Aphasia Depression Rating Score
AE	Adverse Event
ACTRN	Australasian Clinical Trial Registry Number
AQ	Aphasia Quotient (derived from Western Aphasia Battery)
AusTOMS	Australian Therapy Outcome Measures
BNT	Boston Naming Test
CIUs	Correct Information Units
CONSORT	Consolidated Standards of Reporting Trials
CRF	Case Report Form
CTA	Clinical Trial Agreement
DSMC	Data Safety Monitoring Committee
eCRF	Electronic Case Report Form
ECU	Edith Cowan University
FAST	Frenchay Aphasia Screening Test
FDA	Food and Drug Administration
GCP	Good Clinical Practice
GEE	Generalised Estimating Equations
GLMM	Generalised Linear Mixed Model
GP	General Practitioner
IEC	Independent Ethics Committee
IME	Important Medical Event
IQR	Interquartile Range
LMM	Linear Mixed Model
mRS	Modified Rankin Score
MAR	Missing at Random
NHMRC	National Health and Medical Research Council
NIHSS	National Institute of Health Stroke Score
NTA	Neuroscience Trials Australia
OCSP	Oxfordshire Community Stroke Project Classification
RBHOM	Royal Brisbane Hospital Outcome Measure for Swallowing
RCT	Randomised Controlled Trial
SAE	Serious Adverse Event
SAQoL-39	Stroke and Aphasia Quality of Life
SAH	Sub Arachnoid Haemorrhage
SD	Standard Deviation
SDH	Sub Dural Haemorrhage
TIA	Transient Ischemic Attack
TGA	Therapeutic Goods Administration
UC	Usual Care
UTN	Unique Trial Number
VERSE	Very Early Rehabilitation in SpEech

WAB- R	Western Aphasia Battery-Revised
%MPR	Percent of Maximal Potential Recovery

1 Study Design

1.1 Overview

VERSE¹ is a prospective, parallel group, assessor blinded, randomised, multicentre, international clinical trial. Ethics and local governance approval was obtained from all sites participating. Version 3 of the protocol is current at the time of publication. Written, informed consent is obtained from each participant or their legal representative using full hospital approved consent processes supported by aphasia friendly consent documents. All participants in VERSE receive usual ward based care. Participants are randomised in a ratio of 1:1:1 to one of three groups (i) usual ward care alone (UC); or (ii) usual ward care plus high intensity aphasia therapy (UC-Plus); or (iii) usual ward care plus high intensity aphasia therapy (VERSE). The distinguishing features of each of these arms is described in Section 1.5.

1.2 Aims and hypotheses

The primary aim of the VERSE trial is to determine whether very early daily aphasia therapy (UC-Plus and VERSE groups) is superior to usual ward care at 12 weeks post stroke. The secondary aim is to test whether a standardised intense aphasia therapy regimen (VERSE) is more effective and cost effective than non-standardised intense aphasia therapy (UC-Plus). Participants are recruited within the first 14 days following stroke. For the purposes of this trial, aphasia therapy refers to direct aphasia treatment designed to change the communication performance of the person with aphasia. All analyses herewith include only direct aphasia therapy which does not include patient/family counselling and education, case management or documentation.

Primary Hypothesis:

Very early aphasia therapy will result in greater improvement in communication at 12 weeks poststroke, as measured by the Western Aphasia Battery-Revised; Aphasia Quotient (WAB-R (AQ)).²

Secondary Hypotheses:

- 1. VERSE aphasia therapy will result in a greater improvement in communication than UC-Plus aphasia therapy at 12 and 26 weeks post stroke, as measured by the WAB-R (AQ).²
- 2. VERSE aphasia therapy and UC-Plus will each result in greater improvements in communication than UC alone, as measured by the WAB-R(AQ)², at 12 weeks and 26 weeks post stroke.
- 3. VERSE aphasia therapy will result in greater improvements in connected speech than UC-Plus, as measured by Discourse Analysis, at 12 weeks and 26 weeks post stroke.
- 4. VERSE aphasia therapy and UC-Plus will each result in greater improvements in connected speech than UC alone, as measured by Discourse Analysis, at 12 weeks and 26 weeks post stroke.
- 5. Very early aphasia therapy (UC-Plus and VERSE) will result in better quality of life at 12 and 26 weeks post stroke than UC control.
- 6. Very early aphasia therapy (UC-Plus and VERSE) will be more cost-effective than UC at 12 and 26 weeks post stroke.

1.3 Patient Population

Participants include patients with acute stroke and aphasia screened using the shortened Frenchay Aphasia Screening Test.³ Participants are identified, recruited, randomised and assessed within 14 days of stroke. Therapy commences the day after this assessment.

1.3.1 Inclusion Criteria

Patients are eligible if the following inclusion criteria are met:

- The patient has acute aphasia of any type resulting from an acute stroke (ICD 10 codes 161 164 i.e. no TIA, SAH or SDH);
- The patient has a score of less than 93.7 of the Aphasia Quotient of the Western Aphasia Battery-Revised²
- The patient is deemed medically stable at recruitment
- The patient can maintain a wakeful alert state for 30 consecutive minutes within 14 days of stroke onset
- The patient has normal or corrected hearing and vision
- The patient is at least 18 years old; there is no upper age limit for inclusion.
- Informed consent is obtained from the patient or person responsible

1.3.2 Exclusion criteria

Patients are excluded from the study if they have any of the following:

- Pre-existing aphasia before the stroke event
- Have suffered a head injury or have had or require neurosurgery (clot retrieval surgery is not an exclusion if patient is stable post operatively and meets the above criteria)
- Pre-existing clinical diagnosis of dementia
- Diagnosis or treatment of major depression at the time of enrolment
- Concurrent progressive neurological disorders
- Unable to participate in English based therapy due to English being a second language.
- Is participating in another intervention trial, which in the opinion of the VERSE trial manager, may interfere with the outcome of the VERSE trial.

1.4 Randomisation

Participants are randomised to one of three groups (UC, UC-Plus, VERSE) via a central allocation system in a 1:1:1 ratio. Randomisation is stratified by aphasia severity on the WAB-AQ² (Severe: WAB-AQ² 0-31.2; Moderate: WAB-AQ² 31.3-62.5; Mild: WAB-AQ² 62.6-93.7). A remote, web-based, computer-generated randomisation procedure is used. All online data submissions are secured by use of password site entry and data encryption procedures. Once the site staff submits patient recruitment data, the randomisation allocation is immediately provided back to the investigator.

1.5 Intervention

Participants randomised to one of three arms of therapy receive direct aphasia therapy with a qualified speech pathologist for a maximum period of 25 working days. The three arms are:

[figure not shown]
1 Usual Care: Usual ward based aphasia care provided as per health care site standards.

2 UC-Plus: Usual ward based care for aphasia is provided but using a defined therapy regimen of daily sessions of 45 - 60 minutes; each participant receives 20 sessions (15 - 20 hours of direct aphasia therapy) in addition to usual care.

3 **VERSE intervention:** The intensity of this arm of therapy will match the Usual Care-Plus arm, (20 daily sessions of 45 - 60 minutes duration; 15 - 20 hours of direct aphasia therapy) but the speech and language training is prescribed and standardised according to a separate VERSE intervention protocol, in addition to usual care.

The intervention period for the trial concludes at a maximum of 50 days post stroke or when 20 sessions of aphasia therapy are completed (UC–Plus and VERSE) – whichever comes first. Participants are followed up at 12 weeks and 26 weeks post stroke.

Details of the intervention are provided in the VERSE Trial protocol (IJS, 2016).

Days post stroke (weeks)

Figure 1. Trial timeline

1.6 Baseline and follow-up assessments

All stroke patients with aphasia, who are at least 18 years old, are screened for inclusion in the study. Those screened and deemed ineligible for the study are entered onto a screening log which outlines the reason for non-inclusion. Details of the screening and recruitment procedures, as well as the assessment schedule are included in the main trial protocol.

The assessment timeline is outlined in Figure 1. Baseline assessment occurs no earlier than two days from the onset of stroke and no later than 14 days from the onset of stroke. Participants undergo the (AQ) component of the WAB-R.² Participants are also assessed for their medical and stroke history. Baseline data collection includes the collection and documentation of:

- 1) Demographic details including age, gender, past medical history, languages spoken, education level, handedness, employment, Aboriginal or Torres Strait islander status and living arrangements.
- 2) Stroke type and severity (type, hemisphere, first or recurrent stroke, National Institute of Health Stroke Scale, (NIHSS⁴), modified Rankin Scale (mRS⁵), Oxfordshire Community Stroke Project Classification (OCSP⁶), Royal Brisbane Hospital Outcome Measure for Swallowing (RBHOM⁷) and Australian Therapy outcome measures (AusTOMS⁸).
- 3) Additional baseline assessments including the Boston Naming Test (BNT⁹), the "clock drawing" cognitive sub test, and discourse collection.
- 4) Time of assessment and aphasia therapy commencement.

Therapy commences the day after the baseline assessment, and is completed within a maximum of 25 working days and must be completed by day 50 post stroke.

The participants are followed up at their place of residence or in the hospital clinic by a blinded assessor, 12 weeks and 26 weeks after the date of the stroke. Patient assessments at these follow-up visits include:

- the Aphasia Quotient component of the Western Aphasia Battery-Revised²
- the Boston Naming Test,⁹
- Discourse collection,¹⁰⁻¹⁶
- Stroke and Aphasia Quality of life questionnaire 39 item version¹⁷; and
- The Aphasia Depression Rating Scale.¹⁸

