3.4 Patient Characteristic and baseline comparisons

Baseline participant and stroke characteristics will be presented for each of the three groups: UC, UC-Plus and VERSE (Table 1). These will include: age, gender, geographic region (Australia/NZ), stroke risk factors, stroke type, stroke severity (NIHSS),⁴ mRS,⁵ time to randomisation and baseline assessment. Baseline communication, cognition and swallowing characteristics will be presented in Table 2 and will include Aphasia severity, as measured by the WAB-R (AQ),² clock drawing test, Discourse Scores (words, correct information units),¹¹⁻¹⁶ AuSTOMS,⁸ and RHBOMS.⁷

Discrete variables will be summarized as frequencies and percentages. Unless otherwise indicated in the tables, percentages will be calculated according to the number of patients for whom data are available. If there are more than 5% missing values, the denominator will be indicated in the corresponding summary table. Continuous variables will be summarized by the mean and standard deviation (SD) or by the median and interquartile range (IQR). Durations and time intervals will be summarized by medians and IQRs.

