3.5 Primary Outcome: Communication Recovery at 12 weeks by Intensity

3.5.1 Primary Outcome Measure

The primary outcome is improvement in communication at 12 weeks after stroke. Communication outcome will be measured by the WAB-R (AQ).² The WAB-R (AQ) is a comprehensive measure incorporating production of spoken language and auditory comprehension. Improvement will be assessed using the percent of maximal potential recovery achieved (%MPR),¹⁹ which is calculated as the ratio of the difference in WAB-R (AQ)² at 12 weeks and WAB-R (AQ)² at baseline, divided by the difference of maximal attainable score on WAB-R (AQ)² and the WAB-R (AQ)² at baseline. That is,

$$\% MPR \text{ at } 12 \text{ weeks} = \frac{(AQ \text{ at } 12 \text{ weeks}) - (AQ \text{ at } \text{ baseline})}{(\text{Maximum attainable } AQ \text{ score}) - (AQ \text{ at } \text{ baseline})} \text{X}100$$
$$= \frac{(AQ \text{ at } 12 \text{ weeks}) - (AQ \text{ at } \text{ baseline})}{100 - (AQ \text{ at } \text{ baseline})} \text{X}100$$

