The primary aim of this trial is to test the effect of intensity of therapy in early stroke recovery. This is achieved through the primary effectiveness hypothesis which will be analysed using a linear mixed effects regression model with %MPR¹⁶ as the outcome measure. The UC-Plus and VERSE groups will be combined into a single high intensity group. This combined intervention group will be compared to the UC group on the primary outcome measure (%MPR¹⁶ at 12 weeks). The model will adjust for differences in baseline aphasia severity and baseline stroke severity by including the baseline WAB-R(AQ)² score and the baseline NIHSS⁴ score as covariates in the model. The effect of hospital site will be controlled for by including hospital site as a random effect. The treatment effect will be reported as difference in %MPR with the corresponding 95% confidence interval.

Since publication of the trial protocol¹ five new sites have been added to address low participant recruitment. As a result, the Executive Committee decided there was a need to include hospital site as a random effect. This required the adaptation of our original statistical plan from using General Estimating Equations model (GEE) to a Linear Mixed Effect Regression models.

3.5.5 Subgroup Analyses:

The linear mixed effects regression model will be modified to analyse the difference in the primary effectiveness outcome (%MPR¹⁶ at 12 weeks) between

- 1) the VERSE group and UC group AND
- 2) the UC- Plus group and the UC group

As with the primary analysis, the model will adjust for differences in baseline aphasia severity and baseline stroke by including the baseline WAB- $R(AQ)^2$ score and the baseline NIHSS⁴ score as covariates in the model. The effect of hospital site will be controlled for by including recruiting site as a random effect. The main between-group difference at each time point will be assessed through the interaction effect of group and timepoint. The treatment effect for each subgroup analysis will be reported as difference in %MPR¹⁶ with the corresponding 95% confidence interval.

No corrections for multiple testing in subgroup analyses will be undertaken for these planned analyses. The unadjusted p-values will be reported together with the number of subgroup analyses undertaken.

3.6 Secondary Effectiveness Hypotheses:

The following secondary effectiveness hypotheses will be assessed:

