- National Research Council. 2010. The Prevention and Treatment of Missing Data in Clinical Trials. Washington, DC: The National Academies Press. https://doi.org/10.17226/12955.

Appendix 1

Table 1: Baseline Participant and Stroke Characteristics

	UC	UC+	VERSE	All
	n (%)	n (%)	n (%)	n (%)
Recruitment Region				
Australia				
New Zealand				
Patient Details				
Age Median (IQR)				
<65				
65-80				
>80				
Gender				
Male				
Female				
Pre-morbid History (Living arrangements prior to stroke)				
Home alone				
Home with other				
Supported accommodation				
Unknown				
Stroke Risk Factors				
HTN				
IHD				
AF				
Hypercholesterolaemia				
Diabetes				
Smoking				
Baseline NIHSS, Mean (SD)				
Baseline mRS (binary)				
Low (0-2)				
High (3-6)				
High (3-6) Oxfordshire Stroke Classification				

VERSION 1.1 DATE: 28 March 2018

PACS
POCS
LACS
Haemorrhage
Time to Randomisation (days), Median (IQR)*

*n.b. time calculated from stroke onset to randomisation

Page 22 of 29

	UC	UC+	VERSE	All
	n (%)	n (%)	n (%)	n (%)
Frenchay Aphasia Screening Test Median (IQR)				
Baseline Western Aphasia Battery - Revised AQ Mean (SD)				
Ceiling (93.7 - 100)				
Mild (93.6 - 62.6)				
Moderate (62.5 – 31.3)				
Severe (0 – 31.2)				
Baseline Discourse Measures				
No. of Words, Mean (SD)				
No. CIUs, Mean (SD)				
% CIUs , Mean (SD)				
Boston Naming Test, Mean (SD)				
AuSTOMS				
Dysarthria				
No impairment				
Mild impairment				
Moderate impairment				
Moderate/severe impairment				
Profound impairment				
Apraxia of Speech (AoS)				
No impairment				
Mild impairment				
Moderate impairment				
Moderate/severe impairment				
Profound impairment				
Clock Drawing/Cog Test, Median (IQR) RBHOMS				

Table 2: Baseline communication, swallowing and cognition characteristics

Page 23 of 29

		UC	UC+	VERSE	All
Length of Inpatient Hospital Stay* Median (IQR)					
Time to first therapy,* Median (IQR)					
Received Therapy as Inpatient n (%)					
Met Intervention Compliance n (%)					
Intervention number of Therapy	Usual Ward Care				
Intervention number of Therapy Sessions, Median (IQR)+Usual Ward Care Intense TherapyFrequency: Sessions per week, Median (IQR)Usual Ward Care 	Intense Therapy				
Frequency: Sessions per week,	Usual Ward Care				

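### The %MPR models omit days from stroke onset to baseline assessment (2 to 14), a recorded pre-randomisation covariate that could add some precision

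*SAP*

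**What the plan says.** - **Timing of baseline.** Section 1.6: "Baseline assessment occurs no earlier than two days from the onset of stroke and no later than 14 days from the onset of stroke".
- **Timing of outcome.** The same section places follow-up at "12 weeks and 26 weeks after the date of the stroke", so the clock starts at the stroke, not at baseline or randomisation.
- **Outcome.** Section 3.5.1 builds %MPR on "the ratio of the difference in WAB-R (AQ)² at 12 weeks and WAB-R (AQ)² at baseline", divided by 100 minus baseline AQ. Baseline AQ enters both numerator and denominator.
- **Timing is recorded.** The baseline items in 1.6 include "Time of assessment and aphasia therapy commencement". Section 3.4 lists "time to randomisation and baseline assessment" among the characteristics to be shown by arm, and the Table 1 shell in Appendix 1 has a time-to-randomisation row with the note "time calculated from stroke onset to randomisation".
- **Model.** Section 3.5.4 adjusts by "including the baseline WAB-R(AQ)² score and the baseline NIHSS⁴ score as covariates in the model", with hospital site as a random effect. Sections 3.5.5 and 3.6.2 use the same set.
- **Elsewhere.** Randomisation (1.4) is stratified by aphasia severity only. The example predictors for imputation (3.5.3) and the sensitivity analyses (3.10) do not mention timing.

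**The concern.** Two participants with the same baseline AQ, one assessed on day 2 and the other on day 14, may be at different stages of spontaneous recovery and have different time left before week 12. If so, baseline day predicts %MPR beyond what baseline AQ and NIHSS carry, and leaving it out keeps that variation in the residual. The random site effect can absorb only differences in timing between sites.

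What is at stake is precision, and a question that could arise at reporting. Time to randomisation will be published by arm. If the arms happen to differ, readers will ask whether timing explains part of the result, and an adjustment chosen at that stage would be post hoc.

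**Working it through.** **Interval being scored.** With 12 weeks taken as day 84, it is 84 − 2 = 82 days at the longest and 84 − 14 = 70 days at the shortest. The spread is 12 days, and 12/82 = 14.6%. At 26 weeks (day 182) the interval is 168 to 180 days.

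**The plan's own figure.** Section 1.7 gives 246 participants (82 per arm), 80% power, two-sided 5%, a 4.4-point difference and 20% loss. It gives no SD and no within-person correlation, so 246 cannot be reproduced independently. Back-solving for a simple pairwise comparison with 82 × 0.8 = 65.6 analysed per arm:

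SD = 4.4 × √(65.6/2) / (1.960 + 0.842) = 8.99

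This SD is an assumption, not a figure from the SAP. Feeding it back gives 66 per arm (83 after 20% loss). That agrees closely with 82 only because the SD was solved from it.

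**Starting power for the primary contrast.** The primary test pools UC-Plus and VERSE against UC (2:1). SE = 8.99 × √(1/65.6 + 1/131.2) = 1.36, and 4.4/1.36 = 3.235. Power = Φ(3.235 − 1.960) = 89.9%.

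**Gain from the covariate.** If baseline day explains a share R² of the residual variance, the SE is multiplied by √(1 − R²). Power becomes Φ(k/√(1 − R²) − 1.960), with k = 2.802 for a pairwise contrast and 3.235 for the pooled one. The equivalent gain in participants is 246 × (1/(1 − R²) − 1). R² is assumed throughout.

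| Assumed R² | SE ratio | Pairwise power | Pooled 2:1 power | Equivalent participants |
|---|---|---|---|---|
| 0 | 1.000 | 80.0% | 89.9% | 0 |
| 1% | 0.995 | 80.4% | 90.2% | about 2 |
| 2% | 0.990 | 80.8% | 90.5% | about 5 |
| 5% | 0.975 | 82.0% | 91.3% | about 13 |
| 10% | 0.949 | 84.0% | 92.6% | about 27 |

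**Chance imbalance.** Assume baseline day is uniform on 2 to 14 (SD 12/√12 = 3.46 days) and unrelated to AQ and NIHSS. The difference in mean day between 66 UC and 131 pooled participants then has SE 3.46 × √(1/66 + 1/131) = 0.52 days, or about ±1.0 day at 95%. The slope implied by R² is √R² × 8.99/3.46, which is 0.26, 0.58 and 0.82 points per day at 1%, 5% and 10%. An imbalance at the 95% limit would move the estimate by about 0.3, 0.6 or 0.8 points. The 95% CI half-width without the covariate is 1.96 × 8.99 × √(1/66 + 1/131) = 2.7 points.

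**Bias and type I error.** These were checked by simulating an ANCOVA with 66 against 131 analysed (4,000 replicates, residual SD 8.99).
- With a true effect of 4.4 the mean estimate was about 4.4 with and without baseline day, for slopes from 0 to −1.5 points per day.
- Under the null, with a slope of −1 per day, type I error was 4.9% without the covariate and 5.1% with it.
- With a slope of zero, the mean SE was 1.358 without it and 1.361 with it, so an uninformative covariate costs almost nothing.

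**The case against.** A reader might infer that the unequal interval biases the treatment comparison, invalidates %MPR, or lets any imbalance in timing pass in full into the estimate. The documents do not support this.

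- AQ is an eligibility criterion (1.3.1) and sets the randomisation stratum (1.4). Its date therefore precedes allocation, and timing is balanced in expectation.
- All outcome AQs are scheduled at the same time since stroke. Given baseline AQ, %MPR is a linear function of the 12-week AQ. Baseline day is thus one more prognostic variable, not an error in measuring the outcome.
- Chance imbalance in an omitted covariate is already covered by the model's confidence interval. It enters only in proportion to the timing slope, and only for the part not explained by AQ, NIHSS and site.

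It can also be said that the SAP fixes a coherent covariate set and contradicts itself nowhere here, that a marked imbalance would show in the baseline tables, and that the gain rests on an assumed R². At 1% the gain is negligible, and the primary contrast starts near 90% power on the back-solved SD, not 80%.

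All of this stands, and it limits the point to efficiency. It does not remove the point: the variable is recorded, precedes allocation and is plausibly prognostic. Seeing an imbalance in a table is no substitute for having prespecified the adjustment.

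**Conclusion.** The point holds as a low-cost improvement to the analysis, not as an error in the plan. The %MPR models omit a valid baseline covariate while the scored interval varies by 12 days. The treatment effect stays unbiased in expectation and type I error is unaffected; what is lost is some precision and the prespecified handling of chance imbalance in timing.

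The size cannot be fixed from the SAP. The 1% to 10% range for partial R² is assumed, and the pooled-contrast power also depends on the back-solved SD of 8.99. Over that range the gain in power is 0.4 to 4.0 percentage points for a pairwise contrast starting at 80%, and 0.3 to 2.7 for the pooled primary contrast. That a given AQ means something different on day 2 and day 14 is plausible, but the SAP gives no figure for it.

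**What to change.** Before unblinding, add days from stroke onset to baseline assessment as one fixed linear covariate, alongside baseline AQ and NIHSS, in 3.5.4, 3.5.5 and 3.6.2. State the linear form in the text, so that no choice between functional forms is left until the data are seen. Define the day as that on which the baseline AQ was obtained, since 1.8 allows an assessment to run over consecutive days. Include the same variable in the imputation model in 3.5.3, so that the imputed and non-imputed analyses rest on the same covariates.

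The cost is a sentence in each section and one degree of freedom per model. No new data are needed, because 1.6 already has the time of assessment collected.
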